### 4.5 Registration to Correlative and Companion Studies

### 4.5.1 Registration to Substudies described in Section 14.0

There is one substudy within Alliance A221803. This correlative science study must be offered to all patients enrolled on Alliance A221803 (although patients may opt to not participate). This substudy does not require separate IRB approval. The substudy included within Alliance A221803 is:

• The Impact of Ionizing Radiation and Mepitel Film on the Skin Microbiome, Alliance A221803-ST1

If a patient answers "yes" to "My samples and related information may be used for the additional studies described above," Question #1 in the model consent, "I agree that my samples and related health information may be used for the laboratory study described above", they have consented to participate in the substudy described in Section 14.1. The patient should be registered to Alliance A221803-ST1 at the same time they are registered to the treatment trial (A221803). Samples should be submitted per Section 6.2.

### 4.6 Stratification Factors

The randomization routine is found in Section 13.0 (Statistical Considerations). All eligible subjects will be stratified by:

- **4.6.1** Breast reconstruction (yes versus no)
- **4.6.2** Planned boost (yes versus no)
- **4.6.3** Planned bolus (yes versus no)
- **4.6.4** BMI <25.0 versus 25.0-29.99 versus  $\ge$  30.0

### 4.7 Treatment Assignments

After the patient has been registered into the study, the values of the stratification factors will be recorded, and the patient will be assigned to one of the 2 treatment groups using the dynamic allocation procedure which balances the marginal distributions of the stratification factors between the treatment groups.

Patients will be randomized in a 2:1 ratio, favoring the intervention group, to receive:

• Intervention group: Mepitel Film throughout the duration of their radiation

•	Control Group: The existing institutional standard of care throughout the duration of their radiation.

### 5.0 STUDY CALENDAR

**Pre-Study Testing Intervals**: The pre-study testing intervals are guidelines only. Laboratory and clinical parameters during treatment are to be followed using individual institutional guidelines and the best clinical judgment of the responsible physician. It is expected that patients on this study will be cared for by physicians experienced in the treatment and supportive care of patients on this trial.

When calculating days of tests and measurements, the day a test or measurement is done is considered Day 0. Therefore, if a test were done on a Monday, the Monday one week later would be considered Day 7.

To be completed  $\leq$  28 DAYS before registration: History and physical.

	Prior to Registration	Every week, prior to RT	7-14 days post RT	3 months, 6 months, 1 year, and 2 years post RT*	Months 30, 36, 42, 48, 54, 60 months post RT
Tests & Observations					
History & Physical (H&P), weight, height, ECOG PS	X	A		В	В
Acute Toxicities & AE Assessment		X (1)	X (1)	X (1)	
Photographs		C (2)	X (2)	X (2)	
Skin Care Form (App. IV)		X (3)	X (3)	X (3)	
Chronic Toxicities & AE Assessment				X (1)	
Recurrence Assessment				X (4)	
Laboratory Studies					
Serum or Urine HCG		D			
Questionnaires					
mRISRAS ( App.VI - patient and provider completed)		X	X	X	
PRO-CTCAE (App. VII)		X	X	X	
Thin Film Clinical Utilization Survey (App. VIII-Site staff completed)		X			
Correlative Study Skin Swabs	For patients who consent to participate, See Section 6.2 for submission instructions and time points				

- +/- 6 weeks, except for 3 months post RT, +/-2 weeks
- AE assessment includes both CTCAE and non-CTCAE items, See Section 9.1 and Section 9.2.1 for list of AEs and Appendix V for attribution related to non-CTCAE items.
- 2 See Section 6.4, Section 11.3 and Appendix III.
- 3 Completed by site personnel who apply Mepitel Film, See Appendix IV.
- 4 See Sections 6.1.3 and 11.5
- A Prior to week 1 only. H&P does not need to be repeated if done within the past 60 days.

- B Physical exam to evaluate local recurrence is required every 3 months for 1 year and every 6 months (+/- 30 days) from years 2-5 post RT. For years 3 through 5 (months 30 through 60), physical exams may be performed by the patient's local health care provider.
- C Initial photographs are to be acquired prior to the first application of Mepitel Film and no more than 3 days prior to the start of radiation therapy.

  Post-treatment photographs should be acquired upon completion of radiation and prior to removal of Mepitel Film **and** after a minimum of one hour following removal of Mepitel Film.
- D For women of childbearing potential. Must be done within 2 weeks prior to start of RT.

### 6.0 DATA AND SPECIMEN SUBMISSION

### 6.1 Data Collection and Submission

### **6.1.1** Data submission schedule:

A Data Submission Schedule (DSS) is available on the Alliance study webpage, within the Case Report Forms section. The Data Submission Schedule is also available on the CTSU site within the study-specific Case Report Forms folder.

### 6.1.2 Medidata Rave

Medidata Rave is the clinical data management system being used for data collection for this trial/study. Access to the trial in Rave is controlled through the CTEP-IAM system and role assignments.

Requirements to access Rave via iMedidata:

- Active CTEP registration with the credentials necessary to access secure NCI/CTSU IT systems; and
- Assigned a Rave role on the LPO or PO roster at the enrolling site of: Rave CRA, Rave Read Only, Rave CRA (LabAdmin), Rave SLA, or Rave Investigator.

### Rave role requirements:

- Rave CRA or Rave CRA (Lab Admin) role must have a minimum of an Associate Plus (AP) registration type;
- Rave Investigator role must be registered as a Non-Physician Investigator (NPIVR) or Investigator (IVR); and
- Rave Read Only role or Rave SLA must have at a minimum an Associates (A) registration type.

Refer to \_\_\_\_\_\_ for registration types and documentation required.

Upon initial site registration approval for the study in, the Regulatory application, all persons with Rave roles assigned on the appropriate roster will be sent a study invitation email from iMedidata. To accept the invitation, site staff must either click on the link in the email or log in to iMedidata via the CTSU members' website under *Data Management* > *Rave Home* and click to *accept* the invitation in the *Tasks* pane located in the upper right corner of the iMedidata screen. Site staff will not be able to access the study in Rave until all required Medidata and study specific trainings are completed. Trainings will be in the form of electronic learnings (eLearnings) and can be accessed by clicking on the eLearning link in the *Tasks* pane located in the upper right corner of the iMedidata screen. If an eLearning is required for a study and has not yet been taken, the link to the eLearning will appear under the study name in the *Studies* pane located in the center of the iMedidata

Update #03

screen; once the successful completion of the eLearning has been recorded, access to the study in Rave will be granted, and a *Rave EDC* link will replace the eLearning link under the study name.

Site staff who have not previously activated their iMedidata/Rave account at the time of initial site registration approval for the study in the Regulatory application will receive a separate invitation from iMedidata to activate their account. Account activation instructions are located on the CTSU website in the *Data Management* section under the Rave resource materials (*Medidata Account Activation and Study Invitation Acceptance*). Additional information on iMedidata/Rave is available on the CTSU members' website in the *Data Management* > *Rave section* or by contacting the CTSU Help Desk at

**Patient-completed questionnaire booklets** for this study are to be ordered prior to the registration of any patients (see Section 4.3). Samples of questionnaire booklets are available in Appendices VI-VII for reference and IRB submission only. They are not to be used for patient completion. Booklets must be given to patients to complete and patients should be instructed to return the booklets to site staff either in person or by mail and site staff will enter patient and caregiver responses into Rave.

### 6.1.3 Supporting Documentation to be Submitted to the Alliance

This study requires supporting documentation to be submitted through Medidata Rave at the following timepoints:

**Baseline:** Pathology from mastectomy, all operative notes, and any notes documenting post-operative or reconstruction related complications.

**2 years post RT**: All pathology reports and radiology/imaging reports obtained from enrollment through the 2 year post RT follow-up must be submitted to assess recurrence.

### 6.1.4 Data Quality Portal

The Data Quality Portal (DQP) provides a central location for site staff to manage unanswered queries and form delinquencies, monitor data quality and timeliness, generate reports, and review metrics.

The DQP is located on the CTSU members' website under Data Management. The Rave Home section displays a table providing summary counts of Total Delinquencies and Total Queries. DQP Queries, DQP Delinquent Forms, DQP Form Status, and the DQP Reports modules are available to access details and reports of unanswered queries, delinquent forms, forms with current status and timeliness reports. Site staff should review the DQP modules on a regular basis to manage specified queries and delinquent forms.

The DQP is accessible by site staff who are rostered to a site and have access to the CTSU website. Staff who have Rave study access can access the Rave study data using a direct links available in the DQP modules.

CTSU Delinquency Notification emails are sent to primary contacts at sites twice a month. These notifications serve as alerts that queries and/or delinquent forms require site review, providing a summary count of queries and delinquent forms for each Rave study that a site is participating in. Additional site staff can subscribe and unsubscribe to these notifications using the CTSU Report and Information Subscription Portal on the CTSU members' website.

To learn more about DQP use and access, click on the Help Topics button displayed on the Rave Home, DQP Queries, DQP Delinquent Forms, DQP Form Status, and DQP Reports modules.

### 6.2 Specimen collection and submission

For patients registered to substudy A221803-ST1: Skin swab samples will be obtained before and after radiation therapy. All participating institutions must ask patients for their consent to participate in the correlative substudies planned for Alliance A221803-ST1, although patient participation is optional (see Section 6.2.2).

Rationale and methods for the scientific components of this study are described in Section 14.0. For patients who consent to participate, skin swabs will be collected at the following time points for this study:

	Prior to RT	At completion of RT	Storage/ Shipping conditions	Submit to:
For patients registered to A221803-ST1, submit the following: (optional)				
Number of samples to collect:				
Skin swabs (1)	8 swabs*	8 swabs*	Frozen	Mayo BAP Freezer

\* See Section 6.2.2 and Appendix X for detailed collection instructions

1 Skin microbiome analyses described in Section 14.1

### 6.2.1 Specimen Submission Using the Alliance Biospecimen Management System

USE OF THE ALLIANCE BIOSPECIMEN MANAGEMENT SYSTEM (BioMS) IS MANDATORY AND ALL SPECIMENS MUST BE LOGGED AND SHIPPED VIA THIS SYSTEM.

BioMS is a web-based system for logging and tracking all biospecimens collected on Alliance trials. Authorized individuals may access BioMS at the following URL:

using most standard web browsers (Safari, Firefox, Internet Explorer). For information on using the BioMS system, please refer to the 'Help' links on the BioMS webpage to access the on-line user manual, FAQs, and training videos. To report technical problems, such as login issues or application errors, please contact:

For assistance in using the application or questions or problems related to specific specimen logging, please contact:

Sample collection kits must be ordered thought BIOMS. Please log into BioMS and click on "Kit Requests" to order Skin swab collection kits.

After logging collected specimens in BioMS, the system will create a shipping manifest. This shipping manifest must be printed and placed in the shipment container with the specimens.

All submitted specimens must be labeled with the protocol number (A221803), Alliance patient number, patient's initials, date of procurement and type of specimen collected (e.g., skin swabs), as well as the code specifying location of sample (e.g. S-1, S-2, etc. – see Appendix X).

A copy of the Shipment Packing Slip produced by BioMS must be printed and placed in the shipment with the specimens.

Instructions for the collection of samples are included below and in Appendix X. Please be sure to use a method of shipping that is secure and traceable. Extreme heat precautions should be taken when necessary.

Ship specimens Monday through Friday frozen on dry ice, overnight. Do not ship specimens on Saturdays.

Batch shipments are not allowed. **Specimens must be frozen within 2 hours of collection and shipped the same day as collection.** All samples should be shipped frozen. Avoid freeze-thaw cycles. Samples will be placed in long term storage at -80°C upon receipt by the Alliance Biorepository at Mayo Clinic.

All specimens should be sent to the following address:

### 6.2.2 Swab collection Procedures

For all patients who consent to participate, (model consent question, "I agree to have my specimen collected and I agree that my specimen sample and related information may be used for the laboratory study described above"), skin swab samples will be used for the microbiome studies described in Section 14.1. These samples should be collected prior to the initiation of radiation treatment and at completion of radiation treatment. Samples should be obtained as detailed below and in Appendix X and shipped frozen according to Section 6.2.1.

Label samples with the following identification:

- 1) Procurement date/time of collection
- 2) Alliance patient number
- 3) Patient initials
- 4) Alliance study number (i.e., A221803-ST1)

### Preparing for swab collection for patients on the standard of care arm:

- 1. Make sure to review which side will be receiving treatment (right vs left). Review patient randomization to confirm patient is randomized to institutional standard of care arm. Please see Appendix X and follow instructions during collection of skin swabs.
- 2. Collect swabs as directed in Appendix X.

# Preparing for swab collection and Mepitel Film application for patients on the Mepitel Film arm:

- **3.** Make sure to review which side will be receiving treatment (right vs left). Review patient randomization to confirm patient is randomized to receive Mepitel Film. Please see Appendix X and follow instructions during collection of skin swabs, and Mepitel Film application.
- 4. Mark the skin with non-permanent marker to outline area where the Mepitel Film will be placed. These marks will help ensure the swabs are collected from the

correct areas of skin. Mark the contralateral breast/ chest wall where the small control square of Mepitel Film will be placed.

**5.** Collect swabs as directed in Appendix X.

### **Swab collection technique:**

### Equipment:

- 8 swabs
- Sterile Gloves
- 1 pre-filled sterile saline syringe

### Collection:

- 1. Arrange patient in comfortable treatment position with skin exposed.
- 2. Arrange tubes.
- 3. Arrange diagram for guidance.
- 4. Open sterile gloves and use paper for semi-sterile field.
- 5. Open syringe and expel small amount of saline to get it started.
- 6. Open first swab, moisten tip with 4-5 drops sterile saline.
- 7. Shake swab gently to eliminate excess saline.
- 8. Hold pre-moistened swab at approximately 45-degree angle to the skin and swipe area with 20 swipes (one swipe = one direction back and forth would equal two swipes, so 20 swipes is equal to 10 back and forth swipes). Swipe length should be approximately 5 cm. Use firm, even pressure. The swab tip is fairly flimsy, so it will only allow a certain amount of pressure. Most importantly, keep pressure and swab technique uniform across swab collections and across patients.
  - \*\* Please note that when collecting final swabs, the intended collection area may be affected by moist desquamation. In these cases, collect the skin swab from the immediately adjacent intact skin, rather than directly from the area of moist desquamation. In cases of moist desquamation, also collect a 9th swab from the area of moist desquamation. In severe cases, omitting a particular skin swab is allowed at the discretion of the investigator.
- 9. Re-cap swab in tube, and double check it is appropriately labeled.
- 10. Repeat #6-9 until all 8 swabs are collected.
- 11. Transfer tubes into -20°C freezer or dry ice within 2 hours of collection.

**Please note**: All 8 swabs collected from the same patient at the same time point should be placed in one biohazard bag and shipped according to IATA guidelines on sufficient dry ice by overnight mail to the Alliance Biorepository at Mayo Clinic. (Section 6.2.1)

12. Samples should be mailed on dry ice same day, overnight. Avoid freeze thaw cycles. Samples will be accessioned into the Alliance Biorepository at Mayo Clinic (Mayo BAP) for long term storage at -80°C.

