# 14.2.2 Objectives

- a) To determine the impact of ionizing radiation on the skin microbiome, including quantitative analysis of *S. aureus*.
- b) To determine the effect of Mepitel Film on the skin microbiome, including quantitative analysis of *S. aureus*.
- c) To determine the impact of Mepitel Film on radiation-induced changes in the skin microbiome, including quantitative analysis of *S. aureus*.

d) To correlate the aforementioned alterations in the skin microbiome with the observed severity of radiation dermatitis.

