#### Swab collection # 2 (FINAL), LEFT SIDED TREATMENT

#### With Reconstruction

#### No Reconstruction

Location: Please collect 8 swabs from the areas outlined by the 'X' on the adjacent diagram. There will be two collection times during the study, with eight swabs being collected at each collection time.

Collection 2 (Final): 8 samples collected after Mepitel is removed, following final radiation.

Pre-label tubes as follows, with 'F' referring to 'Final.'

F-A, F-B, F-C, F-D / F-1, F-2, F-3, F-4

Swabs obtained from the patient's RIGHT side should always be marked A, B, C, D as follows:

- A Right axilla
- B Right Lateral breast mound/chestwall
- C Right Inframammary fold or corresponding area on the chestwall for non-reconstructed patients.
- D Right medial breast mound/chestwall

Swabs obtained from a patient's LEFT side should always be marked 1, 2, 3, 4 as follows:

- 1 Left axilla
- 2 Left Lateral breast mound/chestwall
- 3 Left Inframammary fold or corresponding area on the chestwall for non-reconstructed patients.
- 4 Left medial breast mound/chestwall

[figure not shown]
The labeling should be identical regardless of whether the patient is receiving right or left sided treatment.

Mepitel Film will be removed prior to final swab collection, so you will have to plan accordingly and ensure the area you are swabbing was covered by Mepitel Film if intended.

[figure not shown]
NCI Version Date: 10/04/2023

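### Where moist desquamation is present, final skin swabs are moved without a flag and the ninth swab has no location code, so the microbiome-severity and film comparisons may be biased in a way the data cannot reliably show

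*Combined protocol and SAP*

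**What the plan says.** **Collection rule (Section 6.2.2, Collection).** If the intended area has MD at the final collection, staff are to "collect the skin swab from the immediately adjacent intact skin, rather than directly from the area of moist desquamation". The same note continues: "In cases of moist desquamation, also collect a 9th swab from the area of moist desquamation". It ends: "In severe cases, omitting a particular skin swab is allowed at the discretion of the investigator".

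**Counts.** The table in Section 6.2 gives eight swabs at each time point, and the equipment list in Section 6.2.2 also gives eight. The repeat step reads "Repeat #6-9 until all 8 swabs are collected", and the shipping note reads "All 8 swabs collected from the same patient at the same time point should be placed in one biohazard bag".

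**Labels.** Section 6.2.1 requires the specimen label to carry identifiers "as well as the code specifying location of sample", and refers to Appendix X for the codes. For the final collection, Appendix X lists "F-A, F-B, F-C, F-D / F-1, F-2, F-3, F-4" for both left-sided and right-sided treatment. The shorter label list in Section 6.2.2 (date and time, patient number, initials, study number) has no location item.

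**Use of the swabs.** Objective c in Section 14.2.2 concerns the effect of the film on radiation-induced microbiome change. Objective d is "To correlate the aforementioned alterations in the skin microbiome with the observed severity of radiation dermatitis". Section 14.2.3 names beta-diversity, taxonomy and phylogeny. It gives no method for the correlation and no rule for moved, omitted or ninth swabs.

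**The concern.** The collection scheme relies on knowing where each swab came from. Start and final codes match site by site, and on the film arm the skin is marked so that swabs come from the right places. At an MD site the final swab comes from different skin but carries the same code as a swab taken where intended. The one specimen from the diseased skin cannot be tied to a site, and if several sites have MD the text does not say which one it represents. In severe cases a swab may be missing, and Section 6.2.2 does not ask for the omission to be recorded.

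Sampling is therefore altered by the outcome under study. Section 1.3 expects less severe dermatitis with the film, so swabs would be moved more often in controls. That brings objective c into question as well as objective d. There is also an arm-specific complication. Under Section 7.2.2, film over an MD area may be removed and is not put back there, and the area is treated by local standard of care. In a film patient, the ninth swab may therefore come from uncovered, treated skin while the moved swab comes from covered skin.

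**Working it through.** **1. Swabs against codes.** Start collection: 8 swabs, 8 codes. Final collection with MD: 8 + 1 = 9 swabs against 8 codes, so one swab has no code. If one site swab is omitted and the MD swab is taken, 8 - 1 + 1 = 8, so a bag of eight does not prove a complete site set.

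**2. What is recorded about each site.** Provider mRISRAS (Appendix VI) scores MD as a share of the whole treatment area, so it does not give the skin state at each swab site. Nothing in Section 6.2.2 or Appendix X asks staff to note a move.

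**3. Direction of bias.** The documents give no effect size, variance, sample size or consent rate for the substudy, so there is no plan figure to reproduce. The following is an illustration; every input is an assumption.

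- 200,000 patients, four treated-side sites each. Severity S is standard normal. Site reaction is r = 0.8 S + 0.6 × noise.
- MD is present where r exceeds a cut-off k, set so that 30% of sites are affected (54% of patients have at least one).
- Change at the intended site = 0.5 r + d × (MD present) + noise with SD 1. The MD-specific shift d is 0, +1 or -1 SD.
- Change in adjacent skin = 0.5 [k + a (r - k)] + fresh noise. Adjacent skin carries a share a = 0, 0.5 or 1 of the excess reaction.
- Outcome: correlation of the patient's mean change with S.

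Check of the reference value with d = 0: covariance 0.5 × 0.8 = 0.40; variance 0.40² + (0.5 × 0.6)²/4 + 1/4 = 0.16 + 0.0225 + 0.25 = 0.4325; correlation 0.40/√0.4325 = 0.61, as simulated.

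Ranges run over a = 0 to 1:

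| MD-specific shift | All at intended site | Moved swabs only | Moved, 50% of MD-site swabs omitted | Ninth swab used at its known site | Ninth swab pooled without a site |
|---|---|---|---|---|---|
| none | 0.61 | 0.47-0.61 | 0.42-0.54 | 0.54-0.61 | 0.55-0.65 |
| +1 SD | 0.75 | 0.47-0.61 | 0.42-0.53 | 0.62-0.67 | 0.61-0.69 |
| -1 SD | 0.22 | 0.47-0.61 | 0.42-0.53 | 0.43-0.52 | 0.46-0.58 |

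With 15% of sites affected and no shift, moved swabs only give 0.55-0.61 against 0.61.

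**4. Reading.** With no shift, or a shift in the same direction, moving swabs lowers the correlation or leaves it unchanged, and omission lowers it further. With an opposite shift, for example after topical antimicrobial treatment, it is overstated. Knowing the site of the ninth swab recovers part or all of the loss when there is no shift, and part of the discrepancy in the other two cases.

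**The case against.** The strongest reply is that the diseased skin is sampled. The ninth swab is additional, so a reader who infers that the worst skin is replaced by better skin, or by nothing, goes beyond the text. Omission is limited to severe cases and does not apply wherever MD occurs. Both points stand.

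Second, other data help. Photographs are required at the end of radiation, close to the final swabs (Sections 7.2.1 and 7.2.2). All specimens are logged in BioMS, so an extra specimen or a missing code may identify an affected patient. Data forms outside these documents may record more. It would therefore be too strong to say that the problem cannot be repaired afterwards. Recovery is only partial, however: a photograph may show MD but not where a swab was taken.

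Third, adjacent intact skin has a rationale. It keeps the film-covered comparison on the film arm, whereas MD areas may have lost film and received soaks, creams or dressings (Sections 7.2.1 and 7.2.2, Appendix IX). This stands, and it argues against making the MD swab the main analysis.

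Fourth, Section 14.2.2 states no site-level pairing. That is correct; the matched codes suggest pairing but do not fix it. The missing rule is part of the gap.

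Finally, a reader might apply the cited MD rates (43.8% and 66.7% in Section 1.2, up to 73% in Section 1.1) to the 72 planned controls to count affected patients. The documents do not support that. These are patient-level rates not tied to a swabbed site at the last fraction, Section 1.4 says the reaction frequently peaks 7-14 days after treatment, and consent to the substudy is optional.

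**Conclusion.** The concern holds in a limited form. As written, sampling at the final collection depends on dermatitis severity, moved swabs look like ordinary ones, and the ninth swab has no code although one is required. The eight-swab counts contradict the instruction to take a ninth. Objectives c and d may therefore be biased, and the data as labelled cannot reliably show whether or how.

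A tempting stronger conclusion is that the association is biased toward no effect. That is plausible if only the eight coded swabs are analysed and adjacent skin reacts less. It is not established: the documents fix neither the analysis nor the swabs that enter it, and the illustration gives no bias, or bias away from the null, under other reasonable inputs. The size depends wholly on the assumed inputs shown above, including omission at random among MD sites.

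The consequence is confined to an optional substudy whose stated aim (Section 2.4.1) is to collect swabs for future analysis. No primary, secondary or safety endpoint is affected. The change is still worth making because swab location is best captured at collection and the remedy is cheap.

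**What to change.** In Section 6.2.2 and Appendix X:

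- Give the MD swab the code of the site it came from plus a suffix, for example `F-B-MD`. Add location to the label list in Section 6.2.2.
- Correct the eight-swab counts in the Section 6.2 table, equipment list, repeat step, shipping note and Appendix X, and put a spare swab and label in the kit.
- Record each final swab as *intact*, *adjacent to MD* or *omitted*.

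In Section 14.2.3, state before sequencing that objective d will be reported both with the adjacent-skin swab and with the MD swab at affected sites. Do not fix the MD swab as the main analysis. Sequencing follows the end of accrual and the last swabs, so this rule can be set before the data exist. For any swabs already collected, photographs and BioMS records can be used as far as they go.

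Cost: a label and kit revision, one tick-box per final swab and some extra analysis. The MD swab is already required, and neither patient care nor the choice of skin to swab changes.
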